11.3.2 Exploratory analysis of diet and brain neurochemistry and functional connectivity

Data from the Harvard food diary obtained at baseline for both FM and healthy control participants will be correlated with molecular (glutamate and GABA) and functional connectivity MR data. A general linear model

will be constructed within SPM having the neuroimaging data be the dependent variable and diet outcomes and group status be the independent variables. As this is an exploratory analysis, no *a priori* hypotheses are made.

11.4. Handling of missing data: Reasons for missingness will be analyzed using multinomial logistic regression with treatment as one of the covariates. The results of formal missing data imputation by predictive-matching algorithms will be compared to the results of missing data exclusion in a sensitivity analysis.

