2. SYNOPSIS

Study Title	Neuroimaging Approaches to Deconstructing Acupuncture for Chronic Pain
Study Sponsor	National Institutes of Health, National Center for Complementary and Alternative Medicine Grant Number: R01AT007550
Study Objective	To evaluate the impact of acupuncture-induced somatosensory afference on altered neurobiology and analgesia in FM.
Study Design	This study design has two components: 1) a cross sectional assessment of brain chemistry, connectivity and response to pain in healthy controls and age- and sex-matched fibromyalgia patients, and 2) a longitudinal assessment of the same fibromyalgia patients randomized to either electro-acupuncture (EA) or mock laser acupuncture (ML).
Study Interventions	Electro acupuncture and mock laser acupuncture. Treatments will be delivered at 2x/week for 4 weeks, for a total of 8 treatments.
Study Duration	The study duration for healthy controls will be 1 week, with a 4 week screening window. The study duration for fibromyalgia patients will be up to 10 weeks: 4- week screening window prior to baseline; 1-week of baseline, 4 week treatment period, and 1 week of follow up.
Sample Size and Population	We will evaluate 40 healthy controls and 80 fibromyalgia patients (n=40 EA and n=40 ML). Demographics will be representative of the population of southeastern Michigan.

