Statistical Analyses	
Cross-sectional analyses will include a comparison of FM patients with HC with respect to GABA, Glx and other neuroimaging biomarkers (t-tests, linear regression);
 
Longitudinal analysis will study treatment effects on within-patient change in neuroimaging biomarkers and changes in clinical pain (t-tests, linear regression with change as a response, linear mixed model with biomarker as a response); treatment and biomarker predictive effects at baseline on clinically relevant 50% reduction of pain as a binary response (logistic regression); the effects of treatment and biomarker baseline measurements on within-patient change in DMN-insula connectivity; biomarker mediation analysis for the treatment effect.
 
In order to screen neuroimaging biomarkers that respond to treatment (show reduced DMN-insula connectivity), interim testing for futility will be performed.
 
Reasons for missingness will be analyzed using multinomial logistic regression with treatment as one of the covariates. The results of formal missing data imputation by predictive-matching algorithms will be compared to the results of missing data exclusion in a sensitivity analysis.

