This aim evaluates a *mechanistic* value of the neuroimaging biomarkers by studying their response to treatment and correlation between the change in biomarker measurements and changes in pain induced by treatments, and biomarker mediation effects.

Hypothesis 1: EA, which involves greater somatosensory afference, will more readily reduce resting insula connectivity to SMN and DMN compared to ML. The change in pain will correlate with change in insula connectivity for EA, but not ML. Insula connectivity will represent a mediator for the treatment effect.

Treatment effects on connectivity

We will perform dual-regression ICA with group level estimates for baseline and post-treatment fcMRI data (DMN and SMN) entered into a linear mixed model with factors STIM (levels EA, ML) and TIME (levels baseline and post-therapy). Time by treatment interaction effect will be of main interest in the analysis. If a significant main effect or interaction is found, we will perform post-hoc difference map analyses, to evaluate which group produced the greatest change in resting connectivity.

Power analysis for fcMRI is based on data from the preliminary study on intrinsic connectivity and its short-term response to acupuncture. From preliminary data on 15 subjects, we estimate the SD of the number of voxels activated before and after acupuncture in the default mode independent component to be 2860 and 4559, respectively. The covariance between these before and after counts is 3388878. This implies the standard deviation of the within-subject change in connectivity of $\sqrt{2860^2+4559^2-2*3388878}=4710$. Based on the same data, we find the before and after means to be 7078 and 9844, respectively. Then, a two-sided paired t-test for the presence of change will have the effect size of 0.6 and the power of 95% with 40 patients in the EA group.

Based the similar mean connectivity difference of around 3000 between ML and EA, and the same SD of 4710 we will have 80% power to detect the difference between treatments with respect to the mean within-patient change in connectivity.

Correlation with pain

A linear mixed model will be used to regress BPI pain measurements on the neuro-imaging biomarkers. Correlation between clinical pain and biomarkers is the primary target.

We hypothesize a correlation coefficient of at least 0.5 between pain and connectivity z score in the EA arm. This will give us 94% power to detect the correlation.

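### The only missing-data sensitivity analysis of the EA-ML estimate compares imputation with exclusion, and agreement between the two cannot rule out bias from outcome-dependent dropout

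*Combined protocol and SAP*

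**What the plan says.** Section 11.4 has two sentences, and the synopsis repeats them. The first is descriptive: "Reasons for missingness will be analyzed using multinomial logistic regression with treatment as one of the covariates". The second is the sensitivity analysis: "The results of formal missing data imputation by predictive-matching algorithms will be compared to the results of missing data exclusion in a sensitivity analysis".

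The documents do not say which of the two methods is primary, which variables enter the imputation, how many imputations are drawn, or what would count as disagreement. They state no expected dropout rate. No delta-adjusted, tipping-point, reference-based, pattern-mixture or selection-model analysis appears anywhere.

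The treatment comparisons at stake are those of Section 11.2 (Aim 2): within-patient change in connectivity, Glx, GABA and evoked-pain response, and BPI pain. The synopsis lists t-tests and regressions on change alongside linear mixed models. The mixed model for connectivity has two time points, baseline and post-therapy.

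**The concern.** Post-treatment imaging is taken only at V12, and post-treatment BPI only at V11 and V12 (Sections 3.1, 9.4.5, 9.4.6). The one symptom score repeated during treatment is the FIQ-R, which Section 10.2 reserves for safety and excludes from research use. For a patient who leaves before V11, an imputation model therefore has little beyond arm and baseline, plus treatment-visit items such as needling sensation and credibility if they are included. Predictive matching then fills the gap with a completer's value, and exclusion uses completers only. If the patients who leave did worse than completers with the same recorded data, neither method can see it.

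Dropout could plausibly differ by arm. EA uses needles with current set between sensory and pain thresholds (Section 9.1.2), while ML involves no skin contact (Section 9.1.3). Follow-up scans may also be lost for pain-related reasons. Analgesic use close to a scan is among the exclusion criteria, eligibility is reviewed again at V12, and the documents do not say how such cases are handled.

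If EA patients who do not improve leave, both planned analyses shift towards EA by a similar amount. Agreement between them would then be uninformative about the bias that matters most for the EA-ML contrast.

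**Working it through.** **1. The plan's own figure.** Section 11.2 gives "SD of the number of voxels activated before and after acupuncture in the default mode independent component to be 2860 and 4559, respectively" and "The covariance between these before and after counts is 3388878". SD of change = √(2860² + 4559² − 2×3388878) = √22,186,325 = 4710. The implied before-after correlation is 3388878/(2860×4559) = 0.26. The treatment comparison is "Based the similar mean connectivity difference of around 3000 between ML and EA, and the same SD of 4710", with 40 per arm. SE = 4710×√(2/40) = 1053, and 3000/1053 = 2.85. A two-sided two-sample t-test at 0.05 (the level is stated under Aim 1 and assumed here) has power 0.803. The claim that "we will have 80% power to detect the difference between treatments with respect to the mean within-patient change in connectivity" reproduces, with all 40 per arm observed.

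**2. What each method needs.** Exclusion is valid if data are missing completely at random, or if missingness depends only on covariates in the analysis model. Imputation is valid if data are missing at random given its predictors. The comparison can therefore detect missingness driven by recorded variables that the analysis omits. Neither covers missingness driven by the unseen outcome.

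**3. Standardised simulation (assumed dropout).** No true effect, 40 per arm, baseline-post correlation 0.5, 20% dropout. Dropout is random in ML. In EA, the log-odds of leaving rise with the residual outcome by the coefficient shown. Imputation is predictive mean matching from baseline and arm. Negative bias favours EA. Ranges span baseline-adjusted and change-score analyses.

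| Coefficient | Bias, both methods (SD) | False positives |
|---|---|---|
| 0.5 | about −0.06 to −0.07 | about 5% |
| 1.5 | about −0.17 | 11-15% |
| 3 | about −0.25 | 19-20% |

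The two methods give the same significance verdict in about 95-98% of trials. With no informative dropout the figure is 97-99%. A separate baseline-adjusted run at coefficient 3 gave false positives of 23-24%.

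**4. On the plan's voxel scale.** Using the SDs and covariance above, with EA non-responders leaving, ML leaving at random and 20% missing:

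| Analysis, true effect | Bias, exclusion | Bias, imputation | Same verdict |
|---|---|---|---|
| Change score, 0 | −1329 | −1138 | 92.5% |
| Change score, 3000 | −1386 | −1176 | 98.1% |
| Baseline-adjusted, 0 | −1208 | −1157 | 95.9% |
| Baseline-adjusted, 3000 | −1251 | −1188 | 99.1% |

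In the first row the methods differ by 191 voxels, 191/1329 = 14% of the bias. The bias is 1138/3000 = 38% to 1329/3000 = 44% of the planned effect, and false positives are 24% and 19%. For comparison, the baseline-adjusted analysis with purely random dropout agrees in 98.5% (no effect) and 95.4% (effect 3000) of trials. Agreement hardly separates biased from unbiased trials. Over 10-30% missing, change-score agreement under this mechanism is 90-97% with no effect and 98% with an effect of 3000.

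**5. A case where the planned comparison works.** Let missingness depend on baseline, in opposite directions by arm, with an unadjusted change score and 20% missing. Exclusion is biased by about 940-960 voxels and imputation by −156 to 11. Verdict agreement falls to 86.5% (no effect) and 74.0% (effect 3000). Putting baseline in the analysis model nearly removes the gap (difference 17-149).

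**6. What a tipping-point analysis would report.** Start from the planned 3000 difference and worsen only the missing EA values by δ. The EA mean moves by (fraction missing)×δ, so significance is lost at δ = (3000 − t×SE)/fraction.

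- 10% missing (36 per arm): SE = 1110, t = 1.994, δ = 786/0.10, about 7900 voxels (1.7 SD of change).
- 20% (32 per arm): SE = 1177.5, t = 1.999, δ = 646/0.20, about 3200 (0.7 SD).
- 30% (28 per arm): SE = 1259, t = 2.005, δ = 476/0.30, about 1600 (0.3 SD).

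**The case against.** Several stronger readings are tempting and are not supported.

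- A reader might infer that the planned check can never show a problem. Step 5 shows that it can, and the change-score analyses the plan names are the kind where it does. It can also diverge when a patient misses the V12 scan but attends V11, because BPI, QST and PROMIS-29 from V11 could then inform the imputation. With an assumed post-treatment predictor correlated 0.5 with the outcome given baseline and seen for all dropouts, bias was −0.19 SD by exclusion and −0.14 SD by matching. The methods separate, but bias remains. This gives no help for patients who miss both visits.
- A reader might infer that both methods rest on one missing-at-random assumption. Exclusion needs more than that, as step 2 sets out.
- A reader might infer that the two estimates will almost always be numerically close. Closeness within 0.1 SD in 99% of trials holds for a baseline-adjusted analysis. With change scores it is about 84%. What persists is agreement of the significance verdicts.
- A reader might infer that the plan adopts agreement as its robustness criterion. It says only that results will be compared.

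The sizes also rest on assumptions. Coefficients of 1.5 and 3 are odds ratios of about 4.5 and 20 per unit of residual outcome, so neither is mild. ML non-improvers leaving would bias against EA. Treatment lasts four weeks, the description of the sham is meant to aid retention (Section 9.1.4), and some loss will be technical, such as QST equipment problems or the Cramér-Rao cut-off. All of this stands as a limit on magnitude. None of it supplies an analysis for outcome-dependent dropout. The reasons model is a useful diagnostic, but it does not bound the bias.

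**Conclusion.** The concern holds in a limited form. The plan's one sensitivity analysis of the EA-ML estimate is informative about missingness explained by recorded data and nearly uninformative about missingness explained by the unrecorded outcome. For patients without V11 and V12, agreement between imputation and exclusion should not be read as evidence against bias.

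The size depends on how strongly dropout follows outcome. Under the step 3 assumptions it is minor at weak dependence, with false positives staying near 5%. It becomes material at the stronger settings, where the false-positive rate is two to four or more times nominal. Dropout rate, mechanism and direction are all assumed, because the documents give none. If follow-up is nearly complete the point has little practical effect. It is worth settling before database lock, while the statistician is still blinded (Section 9.1.1). It is a recommended improvement and does not invalidate the design.

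**What to change.** In Section 11.4, keep the planned comparison and specify the imputation model: arm, baseline values and whatever V11 data are available, with the number of imputations.

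Add a delta-adjusted (tipping-point) analysis for the Aim 2 EA-ML comparisons. Apply it to BPI and to scalar biomarkers: Glx, GABA, and ROI-level connectivity and evoked-pain estimates. Do not apply it to voxel-wise cluster-corrected maps, which cannot simply be shifted. Shift the imputed post-treatment values by arm in steps, for example 0 to 1 SD of change, starting with EA towards no benefit and including shifts in ML. Report the shift at which the conclusion changes, and use the arm-specific reasons for missingness to judge which shifts are plausible. Base the robustness statement on that shift, not on agreement between imputation and exclusion.

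The cost is SAP wording, extra runs of the imputation code and ROI extraction where summaries do not already exist. No new data are needed. The resulting robustness statement may be less favourable than the planned comparison would give.

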12. DATA COLLECTION AND QUALITY ASSURANCE

12.1 Data Collection Forms

All study related information will be collected either via interview with assessments recorded directly onto a case report form, or via self-report questionnaire as per the table below.

FORM NAME	Data Collection Method
Screening & Demographics	
Informed Consent	Study Coordinator/Team Member
Tender Point (1990 ACR FM Criteria)	Study Coordinator/Team Member
FM Survey Questionnaire (FSQ - Wolfe et al 2011 criteria for FM)	Patient
FM Treatment History	Patient
VAS Recall (inclusion) Pain	Patient
Medical History	Patient
Physical Assessment (Height/Weight)	Study Coordinator/Team Member
Urine Pregnancy Test	Study Coordinator/Team Member
HADS	Patient
PHQ-9 (suicidal ideation)	Patient
Socio-Demographics	Patient
Demographics	Patient
Concomitant Medications	Patient
Self-Report	
BPI – Pain Severity and Interference	Patient
FM Survey Questionnaire (FSQ)	Patient
PROMIS - 29	Patient
Perception of Bodily Sensations	Patient
Pain Catastrophizing	Patient
Credibility Scale	Patient
PainDETECT	Patient
Pittsburgh Sleep Quality Index (PSQI)	Patient
MASQ (cognition)	Patient
VAS-Present pain	Patient
Expected Relief Scale (ERS)	Patient
Desire for Relief Scale (DRS)	Patient
Menstrual Questionnaire	Patient
Quantitative Sensory Testing	
Pain Assessment	Study Coordinator/Team Member

After Cuff Questionnaire	Patient Study Coordinator/Team Member
CPM	Member
Visual Stimulation Assessment	Study Coordinator/Team Member
Imaging	
Neuroimaging	Imaging Technician/Patient/Study Coordinator/Team Member
Treatment	
Randomization	Acupuncturist
Assessment of Needling Sensation (MASS)	Patient
Acupuncture Procedure	Acupuncturist
Safety	
Adverse Event form	Acupuncturist/Project Manager/Study Coordinator/Team Member
Fibromyalgia Impact Questionnaire – Revised (FIQ-R)	Patient Project Manager/Study Team Member
Debriefing / Study Exit Form	Team Member

All subjects will be assigned a unique, study-specific identification code. Only the subject ID will be used to associate the subject with source data listed above. Any personal identifiers required to manage the subject while they are participating in the study will be stored separately from the research data files. Those volunteers who do not meet the eligibility criteria or who choose not to participate in the study at either the telephone Pre-Screen or the Screening Visit will be logged. Personal identifiers will be kept until the study has been closed to recruitment, at which time they will be destroyed. This will prevent repeat screenings of potential volunteers.

12.2 Data Management

The University of Michigan Chronic Pain and Fatigue Research Center will be responsible for the collection of all source information. All Case Report Forms will be approved by the University of Michigan IRB.

Participants will complete paper-based questionnaires; no electronic survey completion will occur. Data will be verified and checked for completeness and initialed by the study coordinator or other team member prior to the completion of the visit. All data will be entered into a research database (REDCap) by the study team using double data entry. A blinded team member will enter data into database one, while another study team member will enter the data into the second database. In extenuating circumstances an unblinded study team member may enter data into database two if needed. Each participant’s data will be entered only after the participant has exited the study. Cross-referencing the two databases for disparities will occur annually. Discrepancies will be corrected in REDCap via source document verification.

Study data will be collected and managed using REDCap electronic data capture tools hosted at University of Michigan. REDCap (Research Electronic Data Capture) is a secure, web-based application designed to support data capture for research studies, providing: 1) an intuitive interface for validated data entry; 2) audit trails for tracking data manipulation and export procedures; 3) automated export procedures for seamless data downloads to common statistical packages; and 4) procedures for importing data from external sources.

12.3 Imaging Repository

12.3.1 Pain and Interoception Imaging Network (PAIN)

This trial has a data-sharing agreement with the Pain and Interoception Imaging Network (PAIN), an NCCAM-funded imaging repository at University of California Los Angeles (UCLA). The PAIN initiative is aimed at the characterization of brain signatures associated with chronic pain disorders. The PAIN repository is specifically targeted towards using neuroimaging for discovery of mechanisms and biomarkers related to chronic pain and chronic pain treatment. (<http://pain.med.ucla.edu/>)

12.3.2 Shared Data

High quality structural and resting state functional images taken from the baseline and follow-up imaging sessions (visit 2 and 12) for fibromyalgia participants and from healthy control's sole baseline imaging session (visit 2). In addition to these image files, we will also submit relevant metadata (sex, age, diagnosis). A list of subject IDs and acquisition dates will be provided to UCLA each time data is transmitted.

12.3.3 Confidentiality

All transferred data will be stripped of identifiable information and will be transferred to the PAIN Repository using the SFTP Interface for Archived and Standardized Data. Data are separated from personal identifiers through the use of a code. The code key will be held by the contributor only, and the PAIN Repository will never retain this linking file or have access to the code. The code will be kept in a secure location, which can only be accessed by the research team at the University of Michigan.

12.3.4 Transmission and Storage of Repository Data

The PAIN Repository transfers all data via secure network protocols (https and sftp). Member permissions and provenance are maintained via user and group accounts and a relational database management system. Images are parsed and scanned to both extract scan specifications and ensure long-term file integrity. Algorithmic fingerprint "checksums" protect against digital deterioration (bitrot) by mathematically matching the stored image to the original. Data are stored on a dedicated system separate from user application servers. Only administrators and automated system processes (eg. backup) can access data outside of collaboratively-defined repository datasets. Servers run on NIST Common Criteria compliant Red Hat Enterprise Linux with NSA-developed role-based security (SELinux) enabled. Network security includes firewalls and private local area networks (LANs) with perimeter network (DMZ) access to web servers.

PAIN data are stored in a scalable, secure, fault-tolerant, high availability location at the Oppenheimer Center for Neurobiology of Stress at the University of California, Los Angeles. Data submitted to PAIN will be stored indefinitely.

12.3.5 Accessibility

PAIN data will be used for the purposes of research and analysis, and is accessible by PAIN network authorized investigators only, who have an accepted data sharing agreement and pre-approval from the PAIN Executive Committee (EC).

12.3.6 Participant Authorization

Participants will have the option to decline participation in the PAIN repository portion of the study. A separate section of the informed consent form (ICF) will be reserved for participants to choose whether they agree to participate in the repository by checking "Yes" or "No" and initial. Participants may withdraw their consent to future donation of data to the repository, however any data already submitted to PAIN will not be retractable but will remain coded.

